8.1.1. Order of Assessments

For assessments to be performed at screening visits, refer to the Schedule of Activities in Section 8.9.1.

In case the following assessments are planned to be performed at the same time point, they need to be performed in the following order:

[REDACTED]

2. 12-lead electrocardiogram (ECG) and vital signs;
3. blood sampling for clinical laboratory assessments, [REDACTED]

For other assessments planned to be performed at the same time point, a random order is allowed.

8.1.2. End of Treatment Visit

In countries where filgotinib becomes commercially available, subjects will be requested to attend the EoT visit as soon as possible after the subject has completed at least 48 weeks of treatment (see Section 5.1). For the subjects who have not yet completed 48 weeks of treatment when filgotinib becomes commercially available, the Week 48 visit can replace or occur on the same day as the EoT visit. All assessments listed at the EoT visit can be conducted as part of the Week 48 visit; therefore the EoT assessments do not need to be repeated. If not performed on the same day, there should be a minimum of 1 week and maximum of 4 weeks between the 2 assessments, and the TB assessment at Week 48 suffices for TB assessment at EoT. Other assessments for the EoT visit should be performed according to the Schedule of Activities (Section 8.9).

8.1.3. Re-screening of Subjects

If a subject fails screening, it is allowed to re-screen the subject once. Re-screening may only be conducted after approval from the sponsor's medical lead. When a subject is re-screened, the subject needs to be reconsented and all screening assessments need to be repeated. The subject will be assigned a new subject number.

8.1.4. Unblinding of Subjects at the Study Primary Analysis Time Point

After unblinding at the study primary analysis time point, subjects will receive unblinded treatment and the frequency of study visits will be reduced to every 24 weeks. All subjects should be invited for an unblinding visit no later than 4 weeks after the study primary endpoint unblinding. If no regular visit is scheduled within this time frame, an unscheduled visit should be performed for IP dispensing to ensure the subject has sufficient IP to cover the period until the next 24-weekly visit. Assessments indicated as to be performed every 12 weeks will then be added to the assessments at Week 24.

The unblinded treatment duration depends on commercial availability of filgotinib in the country but will be limited to the maximum study duration for individual subjects of 216 weeks.

8.2. Unscheduled Visits

Additional visits can be performed at other time points for IP dispensing and /or any safety assessments, if clinically indicated. These unscheduled visits and outcomes of additional safety assessments need to be recorded in the source and, if it is a CSP-specified safety assessment performed before the subject's last visit per CSP, also in the CRF.

[REDACTED]

[REDACTED]

[REDACTED]

8.3. Efficacy Assessments

8.3.1. Endoscopy and Biopsy Sample Collection

A sigmoidoscopy will be performed at the visits specified in the Schedule of Activities in Section 8.9.1.

The ES for randomization purposes will be obtained from a sigmoidoscopy performed during the screening period (including biopsy collection for histology assessment). It is recommended that the screening sigmoidoscopy be performed only after the subject meets all other eligibility criteria.

In case of a suspected UC flare, an additional sigmoidoscopy is needed (refer to Section 5.1).

Subjects who discontinue the study prior to Week 48 need a sigmoidoscopy at the ED visit.

The endoscopy will be assessed by a local reader and scored using the Mayo scoring system (refer to Section 8.3.2).

[REDACTED]

[REDACTED]

[REDACTED]

8.3.2. Mayo Clinical Score

The Mayo scoring system for assessment of UC activity is shown in Appendix 2. The total MCS consists of 4 subscores (stool frequency, rectal bleeding, endoscopic findings, and PGA).

The primary efficacy objective will be assessed based on the mMCS. The mMCS is composed of 3 subscores: stool frequency, rectal bleeding, and endoscopic findings.

[REDACTED]

[REDACTED]

Stool frequency and rectal bleeding scores will be established based on the subject's e-Diary. PGA will be completed electronically by the investigator.

A horizontal bar chart consisting of 15 black bars of varying lengths. The bars are arranged in a grid pattern, with some empty spaces between them. The lengths of the bars decrease from top to bottom.

8.3.3.4. IBDQ

This disease-specific questionnaire comprises 32 questions divided into 4 health subscales:

- bowel symptoms (10 questions);
- systemic symptoms, including sleep disorders, and fatigue (5 questions);
- emotional function such as depression, aggression, and irritation (12 questions);
- social function, meaning the ability to participate in social activities and to work (5 questions).

8.4. Safety Assessments

This section describes methods for all safety assessments and recording. Additional assessments (e.g. unscheduled clinical laboratory evaluations or extra vital signs recordings) are allowed to ensure appropriate collection of safety data and to assess any perceived safety concerns. Retesting is allowed in case no results from the assessment(s) are available due to subject-independent external factors, such as, but not limited to, transport and/or technical issues.

Clinically significant abnormal findings should be recorded as AE as indicated in Section 11.1.5.

8.4.1. Adverse Events

The AE reporting period for safety surveillance begins when the subject signs the ICF and ends at their last scheduled visit.

Detailed definitions, reporting period, ratings and reporting requirements for AEs and SAEs are found in Section 11.

8.4.2. Clinical Laboratory Evaluations

The clinical laboratory evaluations (listed in [Appendix 3](#)) will be performed at visits and time points specified in the Schedule of Activities in Section 8.9.1 and Section 8.9.2 (see also Section 8.1, “[Timing of Assessments](#)”). Reference ranges will be supplied by the central laboratory. Clinical laboratory values outside the normal range will be flagged and clinical relevance will be assessed by the investigator. Only laboratory test abnormalities judged as clinically significant by the investigator should be recorded as AEs (see Section 11.1.5). At the discretion of the investigator, when following up AEs, additional laboratory parameters may be tested, and additional samples taken.

Clinical and clinically significant laboratory abnormalities will be managed according to uniform guidelines detailed in [Appendix 4](#).

Blood and urine sample handling, and shipment instructions will be provided in a separate laboratory manual.

8.4.3. Physical Examination

Physical examinations, including height (only during screening) and weight, will be conducted by a physician or a trained physician’s assistant, as acceptable according to local regulation at visits specified in the Schedule of Activities in Section 8.9.1 and Section 8.9.2 (see also Section 8.1, [Timing of Assessments](#)).

Physical examinations will be symptom-directed.

The person conducting the physical examination will document this in the subject’s source documents.

8.4.4. Vital Signs

Vital signs (systolic and diastolic blood pressure, pulse, respiratory rate, and body temperature) will be measured.

Vital signs values will be recorded in a standardized manner at visits specified in the Schedule of Activities in Section 8.9.1 and Section 8.9.2 (see also Section 8.1, “[Timing of Assessments](#)”):

- systolic and diastolic blood pressure and pulse: after the subject has rested in a seated or supine position for 5 minutes;
- respiratory rate;
- body temperature: oral or tympanic (consistent method to be used at every time point within the same subject).

8.4.5. 12-lead Electrocardiogram

At the time points specified in the Schedule of Activities (see Section 8.9.1 and also Section 8.1, “Timing of Assessments”), a 12-lead ECG will be recorded.

12-lead ECG recordings will be performed before blood sampling and after subjects rested for 5 minutes in supine position. In case an indwelling catheter is used, ECGs may be recorded after blood sampling, provided that there is at least 30 minutes between catheter insertion and the ECG recording. When catheter insertion would fail, the 12-lead ECG needs to be taken before the venipuncture and at least 30 minutes after the failed attempt.

The following parameters need to be recorded: heart rate, PR interval, QRS interval, uncorrected QT interval, morphology, and rhythm analysis.

The ECG will be reviewed by the investigator to detect clinically significant abnormalities. This review during the visit needs to be documented in the subject's source documents.

Topic	Percentage
Smart cities	95
Smart homes	92
Smart transportation	90
Smart energy	88
Smart waste management	85
Smart agriculture	82
Smart healthcare	80
Smart water management	78
The concept of a 'smart city'	70
Smart manufacturing	68
Smart retail	65
Smart government services	62
Smart education	58
Smart leisure and tourism	55
Smart sports and fitness	52
Smart arts and culture	48

8.7. Sample Management

8.7.1. Total Blood Volume

The total amount of blood to be taken during the screening and 48-week blinded treatment period for mandatory scheduled laboratory parameters will not exceed 340mL. [REDACTED]

[figure not shown]
The average amount of blood taken for mandatory scheduled laboratory parameters at each subsequent visit scheduled after the 48-week blinded treatment period will not exceed 36 mL.

A limited increase in amount of blood taken is possible in case repeat or unscheduled samples are taken for safety reasons or for technical issues with the samples.

This is considered to be within the acceptable limits based upon the standard of the World Health Organization (WHO, 1994).

8.7.2. Blood and Urine Samples for Routine Safety Tests

All blood and urine samples for routine safety tests (see Section 8.4.2) will be analyzed in a central laboratory and will be destroyed after analysis as per laboratory procedure (unless otherwise indicated in Section 8.8).

8.8. Optional Long-term Storage of Samples and Associated Data for Future Clinical and Research Assessments

Left-over samples from samples already collected during the study and associated data (e.g. sample type, quantity, treatment name) qualify for long-term storage for use as part of future scientific research if subjects have agreed to participate and provide their optional informed consent. Blood (serum and plasma), stool samples, and biopsy samples will be stored. Samples that qualify for long-term storage will be stored for 30 years or according to local legislation, for future scientific research.

The sample(s) and associated data collected for future scientific research will be stored in the Galapagos Biobank and may be used by the sponsor, sponsor partners, and/or other companies contracted by the sponsor. The objective of biobanking is to allow the gathering of additional knowledge on the compound GLPG0634 and/or diseases it may target both investigated during this study and beyond.

No characterization of human genetic material (genes, DNA, or RNA) will be undertaken on these sample(s).

Subjects are not required to consent for the long-term storage of sample(s) and associated data for future scientific research in order to participate in the study. Subjects will also be informed that consent to storage for future scientific research is voluntary and that they may withdraw their consent at any time. If a subject chooses to withdraw consent for the storage of sample(s) and

associated data for future research after the end of the study, then the investigator or designated personnel must inform the sponsor ([contact]).

Withdrawal from the study or [REDACTED] does not, by itself, implicate withdrawal of consent for the storage of sample(s) and associated data for future research. Likewise, withdrawal of consent for the storage of sample(s) and associated data for future research does not implicate withdrawal from the study or [REDACTED]

In the event of subject's death or loss of competence, the already collected sample(s) and data will continue to be used as part of the future scientific research only for the purposes as described in the ICF that was signed by the subject.

The sample(s) and associated data for future research, e.g. body fluids, solid tissue, and derivatives thereof (e.g. protein, peptides) will be destroyed no later than 30 years after the end of the study or according to local legislation. The sample(s) and associated data storage period will be in accordance with the IRB/EC-approved ICF and applicable legislation (e.g. regulatory authority requirements).

The subject will receive additional information specific to the long-term processing of their personal data for future scientific research purposes, as required by the EU General Data Protection Regulation. This includes information about the broader scientific purposes of future research, the lawful bases of the processing activities involved, as well as the retention period of their personal data for these additional purposes. The details are included in the optional ICF.

8.9. Schedule of Activities

For additional information on the timing of the clinical study procedures, please see Section 8.1, “Timing of Assessments”.

8.9.1. Regular Schedule of Activities

EVENT	SCREENING PERIOD		TREATMENT PERIOD						FOLLOW-UP PERIOD	
	S1 ^a	S2	Day 1 ^b	W4	W12 and then every 12 weeks	W24 and then every 24 weeks	W48 ^c and then every 48 weeks	ED	EoT ^d	4 weeks after last IP dose (EoS)
Study Day (D)/ Week (W)										4 weeks after last IP dose (EoS)
	S1 ^a	S2	Day 1 ^b	W4	W12 and then every 12 weeks	W24 and then every 24 weeks	W48 ^c and then every 48 weeks	ED	EoT ^d	4 weeks after last IP dose (EoS)
	D-28 to D-1			± 3 days	± 7 days	± 7 days	± 7 days			± 3 days
Informed consent	✓									
TB assessment ^e	✓ ^f						✓		✓	
Sigmoidoscopy ^g including biopsy collection	✓ ^h						✓	✓ ⁱ		

^a Screening visit 1 (S1) may occur at the same time as any scheduled visit of the SELECTION-LTE study or as a separate visit.

^b Screening visit 2 (S2) and the Day 1 visit can occur on the same day or on 2 consecutive days.

^c After unblinding at the study primary analysis time point, subjects will receive unblinded treatment and the frequency of study visits will be reduced to every 24 weeks with an allowed window of ±10 days (see Section 8.1.4).

^d In countries where filgotinib becomes commercially available, the study will be terminated for the subjects who have already completed at least 48 weeks of treatment.

Subjects will then be requested to attend the EoT visit as soon as possible (see Section 5.1). For the subjects who have not yet completed 48 weeks of treatment when filgotinib becomes commercially available, the Week 48 visit can replace or occur on the same day as the EoT visit. All assessments listed at the EoT visit can be conducted as part of the Week 48 visit; therefore EoT assessments do not need to be repeated.

^e Subjects who have been previously treated for TB with a complete and adequate course of therapy as per local standard of care and as verified by the investigator and do not need to have yearly QuantiFERON® tests should only be screened for signs and symptoms of reactivation at the time of screening and at visits as indicated in the Schedule of Activities.

^f Blood sample for QuantiFERON® test, if applicable, at S1 needs to be taken after signing ICF, preferably 4 weeks before Day 1 to obtain the TB assessment result before randomization. An indeterminate result should be repeated once and the second result (if positive or negative) will be accepted. Subjects who had 2 sequential indeterminate QuantiFERON® tests or a positive QuantiFERON® test during any of the visits of the SELECTION-LTE but do not have active or latent TB at the time of screening, as

EVENT	SCREENING PERIOD		TREATMENT PERIOD						FOLLOW-UP PERIOD	
	S1 ^a	S2	Day 1 ^b	W4	W12 and then every 12 weeks	W24 and then every 24 weeks	W48 ^c and then every 48 weeks	ED	EoT ^d	4 weeks after last IP dose (EoS)
Study Day (D)/ Week (W)				± 3 days	± 7 days	± 7 days	± 7 days			± 3 days
	D-28 to D-1									
Inclusion/exclusion criteria	✓		Prerandomization							
Demographics	✓									
Medical history	✓									
Pregnancy test	✓ ^j			✓ ^j	✓ ^j			✓ ^j	✓ ^j	✓ ^j
FSH test ^k	✓									
Physical examination (symptom-directed)		✓ ^l		✓	✓			✓	✓	✓
Vital signs		✓ ^l		✓	✓			✓	✓	✓
Height	✓									
Weight	✓ ^l			✓	✓			✓	✓	✓

verified by the investigator, or had latent TB and underwent adequate treatment and continued in the SELECTION-LTE, are not required to have a screening QuantiFERON® test. In this case, the subject must be screened for signs and symptoms of TB reactivation.

^g Sigmoidoscopy during screening, at Week 48 and every 48 weeks thereafter, and ED (if applicable), in fasting condition, as per local guidance. In case of a suspected UC flare, an additional sigmoidoscopy is needed. Two biopsies should be collected during every sigmoidoscopy performed during the study.

^h Bowel preparation for screening sigmoidoscopy can only start after signing ICF.

ⁱ Subjects who discontinue the study prior to Week 48 require a sigmoidoscopy at the ED visit.

^j WOCBP only. Serum pregnancy test during screening; urine dipstick pregnancy test at the Week 4 visit, thereafter at the site every 12 weeks, and in-between every 4 weeks at home (±3 days). If a urine test cannot be confirmed as negative (e.g. an ambiguous result), a serum pregnancy test is required to confirm.

^k For postmenopausal women only.

^l Could be taken from SELECTION-LTE. In case assessments listed at S2 are conducted as part of the EoT visit in SELECTION-LTE, the assessments do not need to be repeated and assessment results may be used.

EVENT	SCREENING PERIOD		TREATMENT PERIOD						FOLLOW-UP PERIOD	
	S1 ^a	S2	Day 1 ^b	W4	W12 and then every 12 weeks	W24 and then every 24 weeks	W48 ^c and then every 48 weeks	ED	EoT ^d	4 weeks after last IP dose (EoS)
	D-28 to D-1			± 3 days	± 7 days	± 7 days	± 7 days			± 3 days
Hematology		✓ ^{l, m}		✓	✓			✓	✓	✓
Chemistry		✓ ^{l, m}		✓	✓			✓	✓	✓
Lipid profile (fasted ⁿ)		✓ ^{l, m}				✓			✓	
Urine analysis		✓ ^{l, m}				✓			✓	
HBV DNA monitoring ^o		✓ ^l			✓				✓	
12-lead ECG		✓ ^l					✓		✓	
Serum immunoglobulin		✓ ^l				✓			✓	
CRP		✓ ^l		✓	✓			✓	✓	
Fecal calprotectin ^p	✓ ^q	✓ ^{l,r}		✓	✓			✓	✓	

^m Screening clinical laboratory results may only be available after randomization. In that case, these results will be reviewed after randomization and subjects with laboratory results meeting discontinuation criteria, will be discontinued from the study.

ⁿ Subjects should remain fasted for at least 8 hours, excluding water.

^o Only subjects with positive HBcAb and HBV DNA <LLOQ in a parent UC study will require ongoing HBV DNA monitoring every 12 weeks during the present study, and after study primary endpoint unblinding every 24 weeks.

^p Stool samples need to be taken prior to bowel preparation for endoscopy. Stool samples can be collected within 24 hours prior to the visit or during the visit.

^q FCP should be assessed during screening if the last assessment during SELECTION-LTE was >6 months prior to screening or the most recent value was >250 µg/g.

^r This FCP assessment should be obtained at the EoT visit in SELECTION-LTE (i.e. performed after the subject is fully eligible to roll over to the present study) and will be the baseline of the present study. In case FCP was not obtained at the EoT visit of SELECTION-LTE, an unscheduled stool sample should be collected within 24 hours prior to or during Day 1 (i.e. predose).

EVENT	SCREENING PERIOD		TREATMENT PERIOD						FOLLOW-UP PERIOD	
	S1 ^a	S2	Day 1 ^b	W4	W12 and then every 12 weeks	W24 and then every 24 weeks	W48 ^c and then every 48 weeks	ED	EoT ^d	4 weeks after last IP dose (EoS)
Study Day (D)/ Week (W)	D-28 to D-1			± 3 days	± 7 days	± 7 days	± 7 days			± 3 days
e-Diary instruction & review ^u			✓	✓	✓			✓	✓	✓
modified Mayo Clinical Score ^w	✓						✓	✓		

^a For subjects who consent to participate in the optional PK substudy, PK blood samples will be collected either at the Week 4 or Week 12 visit, or if more convenient, at any

^b Training and dispensation of the e-Diary on Day 1; review subject e-Diary and retrain, if necessary, at all subsequent time points; return of e-Diary at EoS (follow-up visit). Subjects will record the following in the e-Diary: stool frequency, rectal bleeding, and normal stool count.

^c mMCS calculation during screening (baseline value for all subjects), every 48 weeks, and at ED visit (if applicable). Screening mMCS will be calculated using rectal bleeding, stool frequency subscores from SELECTION-LTE during the screening period, and endoscopic subscore from screening sigmoidoscopy. mMCS at other study specified timepoints will be calculated using rectal bleeding, stool frequency, and endoscopic subscores during the present study.

EVENT	SCREENING PERIOD		TREATMENT PERIOD						FOLLOW-UP PERIOD	
	S1 ^a	S2	Day 1 ^b	W4	W12 and then every 12 weeks	W24 and then every 24 weeks	W48 ^c and then every 48 weeks	ED	EoT ^d	4 weeks after last IP dose (EoS)
Study Day (D)/ Week (W)				± 3 days	± 7 days	± 7 days	± 7 days			± 3 days
	D-28 to D-1									
Randomization ^y			✓							
Dispense IP			✓	✓	✓ ^z					
Review IP compliance				✓	✓			✓	✓	
Concomitant medications	✓ ^v		✓	✓	✓			✓	✓	✓
Dose IP			q.d. throughout the treatment period starting Day 1 ^{aa}							✓
AE assessment	✓ ^v		throughout the study ^{bb}							

AE: adverse event; CRP: C-reactive protein; ECG: electrocardiogram; ED: early discontinuation; EoS: End of Study; EoT: End of Treatment; FSH: follicle stimulating hormone; HBV: hepatitis B virus; [REDACTED]; IP: investigational product; [REDACTED]; q.d.: once daily; S1: Screening visit 1; S2: Screening visit 2; TB: tuberculosis; UC: ulcerative colitis.

^y Randomization only after performing all screening procedures and after completion of the EoT visit in SELECTION-LTE.

^z Frequency of IP dispensation after study unblinding at the primary analysis time point will be every 24 weeks.

^{aa} If on Day 1 the subject has already taken the IP as assigned in the SELECTION-LTE study, the first dose as assigned in this study should be taken on Day 2.

^{bb} AEs ongoing at the end of the subject's participation in the SELECTION-LTE study should be recorded as medical history.

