- In case of further worsening of symptoms after Week 2 following re-escalation and/or no improvement in pMCS is detected at Week 4, addition of corticosteroid treatment (i.e. orally- and/or rectally-administered corticosteroids) can be considered with a maximum oral dose of 30 mg q.d. prednisone equivalent.
- If the subject does not respond to re-escalation therapy within a timeframe of maximum 12 weeks, the subject will be permanently discontinued from the treatment and invited to remain in the study up to Week 48 (see [Section 5.4.1.1](#)).
- If subject improvement is sufficient in the opinion of the investigator, the subject will restart the regular Schedule of Activities ([Section 8.9.1](#)), starting from the next 12-weekly visit assessments. The subject may continue on open-label 200 mg filgotinib q.d. until the end of the study. Corticosteroid treatment should be tapered off at the discretion of the investigator.

In case symptoms are worsening again after 12 weeks of re-escalation, the disease worsening criteria must be applied, as explained in [Section 5.4.1.3](#).

Study duration

Each subject will be in the study for a minimum of approximately 56 weeks (28 days screening period + 48 weeks of treatment + 4 weeks follow-up) in countries where filgotinib will become commercially available, and for a maximum duration of 216 weeks (approximately 4 years) in case filgotinib will not become commercially available. In case of re-escalation, the subject will remain in the study at least until the next regular scheduled visit after the 12 weeks post re-escalation visit, or until the end of the study in that country, whichever is longer.

In countries where filgotinib becomes commercially available, the study will be terminated for the subjects who have already completed at least 48 weeks of treatment. Subjects will then be requested to attend the EoT visit as soon as possible. For the subjects who have not yet completed

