6.3. Prohibition and Restrictions

6.3.1. Precautions for Sexual Intercourse

For participation in this study, the use of highly effective contraception is required as outlined below for all female subjects who are of childbearing potential. In addition, during the study women of childbearing potential (WOCBP) must have at minimum a urine pregnancy test every 4 weeks.

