6.3.1.1.2. Contraceptive Methods

Contraception for Female Subjects of Childbearing Potential

The inclusion of female subjects of childbearing potential requires the use of highly effective contraceptive measures. Women must have a negative serum pregnancy test during screening of the present study. Urine pregnancy tests will be performed at monthly intervals thereafter during filgotinib treatment. Female subjects must agree to continue to use one of the following contraceptive methods from screening, during the study, and until the end of the study:

- complete abstinence from intercourse of reproductive potential. Abstinence is an acceptable method of contraception only when it is in line with the subject's preferred and usual lifestyle.

OR

- consistent and correct use of 1 of the following methods of birth control listed below:
 - intrauterine device (IUD) with a failure rate of <1% per year;
 - tubal sterilization;
 - Essure micro-insert system (provided confirmation of success 3 months after procedure);
 - vasectomy in the male partner (provided that the partner is the sole sexual partner and had confirmation of surgical success 3 months after procedure).

Female subjects who utilize a hormonal contraceptive as one of their birth control methods must have consistently used the same method for at least 3 months prior to study dosing.

Hormonally-based contraceptive methods permitted for use in this protocol are as follows:

- oral contraceptives (either combined estrogen/progestin or progesterone only);
- injectable progesterone;
- implants of levonorgestrel;
- transdermal contraceptive patch;
- contraceptive vaginal ring.

All female subjects must also refrain from egg donation and in vitro fertilization during the study and until the end of the study.

The used contraceptive methods for female subjects must be documented in the source documents.

Women of nonchildbearing potential are not required to use any contraceptive method.

For information on the timing and requirements for pregnancy testing or FSH testing, refer to Section [8.4.2](#) and the [Schedule of Activities](#).

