8.1. Timing of Assessments

The study assessments described below will be performed at time points as specified in the Schedule of Activities in Section 8.9.1 and Section 8.9.2.

The ICF needs to be signed before any study procedure, including screening procedure, is carried out.

Subjects in the SELECTION-LTE study who are in clinical remission with 200 mg filgotinib q.d. for at least 2 consecutive quarterly visits, will be provided the option to roll over to the present study at any scheduled visit of the SELECTION-LTE study or at a separate visit.

Subjects will be requested to attend the site for at least 2 screening visits:

- Screening visit 1 (ICF signature) (S1) and other screening assessments as per Schedule of Activities in Section 8.9.1, including TB assessment and screening FCP assessment (if last FCP observation was >6 months prior to screening or most recent FCP value was >250 µg/g) in order to obtain the results prior to randomization.

Depending on the screening FCP in the present study (if applicable) and the ES, the subject will either be a screening failure (FCP >250 µg/g or ES >1) in the present study and will remain in SELECTION-LTE, or the subject will be eligible (FCP ≤250 µg/g and ES ≤1) and will need to perform the EoT assessments in SELECTION-LTE and the remaining screening assessments before being randomized to the present study (refer to Schedule of Activities in Section 8.9.1).

- Screening visit 2 (S2), the EoT visit in SELECTION-LTE, and the Day 1 visit of the present study can occur on the same day or on 2 consecutive days.

Some data collected in SELECTION-LTE, as specified in the Schedule of Activities in Section 8.9.1, may be used in the present study.

In case a randomized subject is not able to attend a scheduled study visit on-site for reasons related to SARS-CoV-2 pandemic restrictions, a phone call or a televisit may be conducted (televisit after obtaining approval from the sponsor). It is strongly recommended to conduct planned study assessments for the applicable visit as per protocol as much as possible. If possible and if local regulations allow, and the subject agrees, trained site study staff are encouraged to perform study assessments at the study subjects' home or a local facility. Only staff trained in conducting the protocol planned assessments are authorized to perform home or local facility visit assessments and the alternative arrangements need to be adequately documented.

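### The schedule lists no pregnancy test at Day 1, so the screening serum result can be up to 28 days old at randomization and protocol-scheduled tests up to 56 days apart (59 with the visit window)

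*Protocol*

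**What the plan says.** Footnote j to the pregnancy-test row of protocol 8.9.1, repeated in SAP 2.4.1, gives the sequence for women of childbearing potential: "Serum pregnancy test during screening; urine dipstick pregnancy test at the Week 4 visit, thereafter at the site every 12 weeks", with 4-weekly home tests between those later site visits. The row has no entry at Day 1.

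The surrounding text is as follows.

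- Inclusion criterion 5 (6.1) requires a negative serum test during screening, with no limit on its age, and agreement to monthly dipsticks while on filgotinib.
- Section 6.3.1 sets a minimum frequency: "during the study women of childbearing potential (WOCBP) must have at minimum a urine pregnancy test every 4 weeks".
- Section 6.3.1.1.2, after the screening serum test, adds: "Urine pregnancy tests will be performed at monthly intervals thereafter during filgotinib treatment". For timing it refers to Section 8.4.2 and the Schedule. Section 8.4.2 adds no pregnancy test.
- Inclusion criterion 2.1 requires subjects to be on filgotinib 200 mg in SELECTION-LTE at entry.
- Footnote l lets several other rows borrow parent-study results: "Could be taken from SELECTION-LTE. In case assessments listed at S2 are conducted as part of the EoT visit in SELECTION-LTE". It is not attached to the pregnancy row.
- The re-escalation schedule (8.9.2) does list a urine pregnancy test at its own baseline.

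**The concern.** Section 5.5 states that filgotinib is contraindicated in pregnancy. Pregnancy is also an exclusion (6.2, criterion 5) and a mandatory reason to stop treatment (5.4.1.1, item l). The eligibility decision does rest on a negative serum test, but that result may be four weeks old when the subject is randomized, and the next test this protocol lists is four weeks later. A pregnancy that begins after the serum test could be found later than it would be with a test at S2 or Day 1, and the woman stays on filgotinib throughout.

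The long interval is not far-fetched. Footnote f prefers the S1 QuantiFERON sample, where one is needed, about 4 weeks before Day 1. A site that draws the serum pregnancy test at the same time lands near the upper end of the range.

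**Working it through.** **Inputs**

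- Screening runs from D-28 to D-1 (8.9.1), with a maximum of 28 days (5.1).
- S2 may fall on the same day as Day 1 or the day before (8.9.1 footnote b; 8.1).
- The Week 4 visit has a window of 3 days either side (8.9.1).
- There is no Day 0 (SAP 4.3.1), and the Week 4 target is Day 29 (SAP 4.3.3). The window is therefore D26 to D32.
- Randomization and first dose are taken to be on Day 1.

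**The plan's own interval.** The 4-week figure in 6.3.1 is 28 days. From Week 4 onward it reproduces: Week 4 to the home test at Week 8 is 57 − 29 = 28 days, and Week 8 to Week 12 is 85 − 57 = 28 days. The interval from screening to Week 4 is the exception.

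**Screening to Week 4.** For a serum test k days before Day 1, the age of the result on Day 1 is k. The gap to a test on day w is k + (w − 1), that is k + 28 at D29, k + 25 at D26 and k + 31 at D32.

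| Serum test | Age on Day 1 | Gap to D29 | Gap to D26 | Gap to D32 |
|---|---|---|---|---|
| D-28 | 28 | 56 | 53 | 59 |
| D-14 | 14 | 42 | 39 | 45 |
| D-1 | 1 | 29 | 26 | 32 |
| S2 held on Day 1 | 0 | 28 | 25 | 31 |

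**Against the 4-week rule.** The text does not settle when the interval starts.

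- Section 5.1 counts screening as study time, with each subject "in the study for a minimum of approximately 56 weeks (28 days screening period + 48 weeks of treatment + 4 weeks follow-up" weeks. Section 6.3.1.1.2 has monthly tests follow the serum test in women already on filgotinib. On this reading 28 days is the limit, and the schedule allows up to 56.
- The same section separates screening from the study when it requires "one of the following contraceptive methods from screening, during the study, and until the end of the study". If the interval starts at Day 1, Week 4 is 29 − 1 = 28 days later (31 with the window), and the rule is nominally met.

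**With the fix**

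- Dipstick on Day 1: D-28 to D1 is 28 days; D1 to D29 is 28 days, or 31 to D32.
- Test on D-1 (S2 or SELECTION-LTE end-of-treatment visit the day before): D-28 to D-1 is 27 days; D-1 to D29 is 1 + 28 = 29 days, or 1 + 31 = 32 to D32.

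**The case against.** **The body text may already require the test.** If the monthly dipsticks in criterion 5 and 6.3.1.1.2 run from the serum test, a serum test on D-28 makes a dipstick due at about Day 1. If the interval starts at Day 1 instead, there is no conflict. This is why a definite breach, which a reader might infer, is not supported. It does not remove the gap: 6.3.1.1.2 sends sites to the Schedule for timing, and the Schedule lists no test there.

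**The parent study may test in this interval.** Footnote y says "Randomization only after performing all screening procedures and after completion of the EoT visit in SELECTION-LTE", and Section 8.1 adds that S2, "the EoT visit in SELECTION-LTE, and the Day 1 visit of the present study can occur on the same day" or on two consecutive days. A pregnancy test at that visit would close most of the gap. The documents do not say whether there is one, so the 56 and 59 days describe this protocol's schedule. To infer that women actually went eight weeks untested would go beyond the documents.

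**S2 is not excluded.** A reader might take the schedule to rule out a test at S2. Footnote j says only that the serum test falls in screening, which includes S2, and the column positions in the extracted tables are too unreliable to decide. A site can comply with a gap of 28 days.

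**The added risk is small.** Day 1 is not the start of exposure, and randomization keeps or lowers the dose. Highly effective contraception is required from screening (6.3.1.1.2), and a woman who is or suspects she is pregnant must report it and stop treatment at once (6.3.1.4). The re-escalation baseline is an imperfect comparator, because there the 100 mg subjects double their dose. All of this stands, and it sets the severity. It is not a reason to leave the interval to an undocumented source.

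**Conclusion.** The point holds as a minor gap in the schedule. The only predose pregnancy test in this protocol can be anywhere from 0 to 28 days old at randomization. The gap to the Week 4 test is 28 to 56 days nominally, and 25 to 59 days with the window. The upper values need a serum test at the very start of a full 28-day screening period.

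This sits poorly with the monthly or 4-weekly testing that criterion 5, 6.3.1 and 6.3.1.1.2 describe for women already on the drug, and with the test at the re-escalation baseline. It is not shown to breach any of them.

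The documents do not give the number of women of childbearing potential. It is at most 80 as planned and at most 22 as randomized (SAP 2.4.3). Efficacy is unaffected. The study was terminated early (SAP 1), so the point mainly matters for the schedule as designed, or if it is reused.

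**What to change.** Add a predose urine dipstick for women of childbearing potential at S2/Day 1 to the pregnancy-test row and to footnote j. Waive it if the screening serum test, or a documented negative SELECTION-LTE end-of-treatment pregnancy test, was done on the same or previous day. One sentence in 6.3.1 saying whether the 4-week interval runs from the screening test or from Day 1 would remove the remaining ambiguity. Repeat the footnote change in SAP 2.4.1.

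The cost is one table entry, one footnote clause and at most one extra dipstick per woman at a visit already taking place. Urinalysis is already listed at S2. Where a same-day or previous-day result is accepted, there is no extra test.
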